### Missing Data:

The analysis will use spirometry data which are consistent with the visit assignment as described in Section 6.4. Subjects who discontinue trial medication should remain in the trial and continue to provide all scheduled FEV1 measurements. The primary analysis will include all available on-treatment and off-treatment period data, regardless of adherence to or discontinuation of trial medication. While all efforts will be made to ensure subjects remain in the trial, the following planned imputation strategy will allow for an appropriate primary analysis in the presence of missing FEV1 data.

To calculate baseline values, missing Visit 1 measurements for the primary efficacy variable (FEV1) will be imputed using Visit 0 (screening) measurements, if available.

Missing post-baseline measurements as a result of withdrawal from the trial for the primary efficacy variable (FEV1) will be imputed using an IUDR methodology. For subjects who withdraw from the trial due to AE, death, physician decision, or lack of efficacy, missing post-baseline FEV1 measures as a result of withdrawal from the trial will be imputed using the baseline FEV1 measurement (BOCF procedure). Missing FEV1 measurements as a result of withdrawal from the trial, where the withdrawal was as a result of other causes (i.e. lost to follow-up, relocation, pregnancy, major protocol deviation, sponsor decision, withdrawal of consent, or other) will not be imputed. Missing data at intermediate visits (i.e. where data is available at a later visit) will not be imputed.

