10 STATISTICAL METHODS

10.1 General considerations

A full description of the statistical methods planned for this trial can be found in the DPM-CF-303 Statistical Analysis Plan (SAP).

Efficacy analyses will be conducted using the intention to treat (ITT) analysis set (refer **Section 10.1.2.1**) as well as the per protocol (PP) analysis set (refer **Section 10.1.2.2**). Safety analyses will be conducted on the safety analysis set (refer **Section 10.1.2.3**).

Significance tests will be performed assuming a two-sided 0.05 significance level; two-sided 95% confidence intervals will also be computed.

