10.1.1 Sample size justification

Enrolment will continue until at least 350 subjects have been randomized to treatment in a 1:1 ratio.

Assuming that the change from baseline in FEV₁ on control is 0 mL and the change from baseline in FEV₁ on mannitol is 80 mL, then a sample size of 350 (175 Mannitol : 175 Control) subjects will yield 90 % power at the 0.05 significance level to detect this difference between the treatment groups assuming a pooled standard deviation of 230 mL. The sample size calculation is based on a t-test of the treatment contrast at week 26. While this approach is not completely concordant with the primary analysis which computes the mean change in FEV₁ over all three post-baseline visits it can be considered a suitable method for estimating sample sizes for longitudinal analyses and is likely to be conservative.

The estimated pooled standard deviation of 230 mL is based on the observed pooled standard deviation in the pooled adult DPM-CF-301 and DPM-CF-302 data from subjects who completed the studies.

This minimum sample size is based upon the observed pooled standard deviation from both DPM-CF-301 and DPM-CF-302 studies in subjects with baseline FEV₁ of more than 40% but less than 90%. However the observed standard deviations were different in these two

previous studies, and were highly influenced by a few outlying values. In addition, the present trial (DPM-CF-303) will be conducted at different sites and in different countries to the previous studies. Thus there is some uncertainty as to what the observed standard deviation is likely to be in this trial (DPM-CF-303). For these reasons a sample size re-estimation is planned to be completed after at least 300 subjects have been recruited and will be based on all available 26-week data. This blinded sample size re-estimation will be based on the method of Kieser and Friede [15] which preserves the overall type 1 error rate. Therefore no adjustments to the overall significance level for the trial is required. See Section 10.1.5 for more information.

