### 7.1.3. Discontinuation from Trial Medication

The number and percentage of subjects who completed the trial on trial medication will be presented for the ITT set.

The number and percentage of subjects who discontinued from trial medication (whether or not they continued in the trial), including a breakdown of the corresponding reasons for discontinuation will be presented for the ITT set. If reason for discontinuation is missing for subjects who withdrew from the trial at the same time as trial medication discontinuation, the reason for withdrawal will be used. In addition, the number and percentage of subjects who discontinued trial medication without off-trial medication efficacy data and the number and percentage of subjects who discontinued trial medication with off-trial medication efficacy data, including a breakdown of the corresponding reasons for discontinuation will be presented for the ITT set. In each case, all reasons for discontinuation listed in the CRF will be included in the summary, whether or not any subjects discontinued for each reason.

For those subjects with off-trial medication efficacy data, the number and percentage of subjects who went on to complete the trial while off trial medication and the number and percentage of subjects who subsequently withdrew early from the trial while off trial medication will be presented for the ITT set.

If applicable, a similar breakdown for subjects who never started trial medication will be presented for the ITT set.

Pharmaxis Ltd

DPM-CF-303

Final v1.0

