## Statistical Analysis Plan

Imputation of missing FEV1 measurements by means of BOCF is a reasonable assumption in studies of adult subjects with cystic fibrosis, as those subjects who discontinue will no longer receive treatment and are thus likely to promptly return to their baseline lung function. Imputation by BOCF specifically inhibits any possible prolongation of an observed early treatment benefit implicitly conferred by a mixed model. Considering the higher drop-out rate observed with the experimental treatment compared to control in previous studies (DPM-CF-301 and DPM-CF-302), BOCF is not likely to favour the mannitol arm.

The primary analysis will target the de facto estimand assessing the effect of a treatment policy (Estimand 1 in Mallinckrodt ) by:

- Including all available on-treatment and off-treatment period data.
- Handling missing data based on a clinically reasonable assumption not biased in favor of the mannitol arm.

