## 8.4. SUMMARY OF ANALYSES

Table 6: Summary of Analyses

Analysis Designation	Endpoint	Model	Imputation Process Used	Off-trial Medication Data Included	Analysis Set
Primary					
Primary	FEV 1 Absolute Change from Baseline	MMRM	IUDR (trial withdrawal reason)/ BOCF	Yes	ITT
Primary - Sensitivity 1	FEV 1 Absolute Change from Baseline	ANCOVA	Pattern Mixture: MI Based on Reasons for Trial Withdrawal	Yes	ITT

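### The primary BOCF rule reads only the reason for leaving the trial, so a mannitol subject already off drug for an adverse event can keep part of a modelled benefit: a small shift towards mannitol

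*SAP*

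**What the plan says.** The primary analysis keeps all observed FEV1 values, on and off drug. Values missing because the subject left the trial are set to baseline under one condition (SAP 8.1.1, Missing Data; same rule in SAP 6.3): "For subjects who withdraw from the trial due to AE, death, physician decision, or lack of efficacy". Other withdrawal reasons, among them loss to follow-up and withdrawn consent, get no imputation. The primary row of Table 6 in SAP 8.4 confirms which reason counts: "IUDR (trial withdrawal reason)/ BOCF". GRP2 of Sensitivity Analysis 1 sorts subjects by the same variable.

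Stopping drug and leaving the trial are separate events. Protocol 9.2 asks subjects who stop drug to stay and attend the remaining visits. Protocol 8.1.2 keeps in the trial those told to take no more study medication after a post-dose FEV1 fall above 20%. SAP 7.1.3 tabulates reasons for stopping drug and also "the number and percentage of subjects who subsequently withdrew early from the trial while off trial medication". Both reasons are therefore on record, and Supportive Analyses 6 and 7 already use the drug-stopping one.

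SAP 8.1.1 justifies BOCF by saying that "those subjects who discontinue will no longer receive treatment and are thus likely to promptly return to their baseline lung function". It adds that BOCF prevents the mixed model from prolonging an early gain, and that the handling of missing data should not be biased towards mannitol.

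**The concern.** Take a mannitol subject who stops drug for an adverse event, stays in the trial, and later leaves by withdrawing consent. The recorded reason for leaving is not on the BOCF list, so the visits missed after leaving go to the mixed model, which borrows from mannitol subjects who mostly remain on drug. SAP 8.1.2 states the matching assumption openly: those who leave for other reasons are taken to go on benefiting as completers do. That cannot describe someone who had already stopped drug for an adverse event.

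At stake is a small credit for visits at which the subject was off drug. It would enter the primary estimate through the same route that the SAP says BOCF is there to close.

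**Working it through.** **1. The plan's own figure.** Inputs from Protocol 10.1 and 10.1.1: "Significance tests will be performed assuming a two-sided 0.05 significance level"; "350 (175 Mannitol : 175 Control) subjects will yield 90 % power at the 0.05 significance level"; the change "on mannitol is 80 mL" against 0 mL on control; "assuming a pooled standard deviation of 230 mL".

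- Per arm: 2 × (1.960 + 1.282)² × 230² / 80² = 173.7, so 174 (348 in total) by normal approximation. The t-test needs 175 per arm (350), with power 0.9005. The plan's figure reproduces.
- Planned standard error of the difference: 230 × √(2/175) = 24.6 mL.

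**2. Which value the model sees.** Suppose the last dose is on Day 29 (Week 4) and the subject leaves around Week 10, so Weeks 14 and 26 are missing.

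- SAP 6.2.7 counts efficacy data as on-treatment up to 7 days after the last dose, here Day 36. The Week 6 visit on target Day 43 is 14 days after the last dose, so it is off-treatment.
- A discontinuation visit held by Day 36 is on-treatment and falls in the Visit 2 window (Day 14 to 70). Under SAP 6.4 it replaces the off-treatment Week 6 value.
- The only value retained can therefore be an on-drug one. If the discontinuation visit is held later, the retained value is off-drug.

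**3. Value implied by the model at a missing visit.** Assumptions: arm mean 80 mL, equal between-visit correlation r = 0.7 (not in the documents), true off-drug change 0 mL.

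- One retained value x: 80 + r(x − 80). For x = 0 (off drug) this is 80 − 56 = 24 mL, with a range of 16 to 40 mL for r from 0.8 to 0.5. For x = 80 (on drug) it is 80 mL.
- On-drug 80 at Week 6, then off-drug 0 at Week 14: 80 − 80 × r/(1 + r) = 80 − 80 × 0.412 = 47 mL at Week 26 (44 to 53 mL for r from 0.8 to 0.5).
- BOCF gives 0 mL in every case.

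**4. Shift in the estimate** = share of mannitol subjects affected × share of the three equally weighted visits missing × implied value. The share affected is not in the documents; 2% to 5% is assumed, with 10% as an outer case.

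| Retained values | Visits missing | Implied value | 2% | 5% | 10% |
|---|---|---|---|---|---|
| Off-drug Week 6 at 0 | 2 of 3 | 24 mL | 0.3 mL | 0.8 mL | 1.6 mL |
| On-drug Week 6 at 80, off-drug Week 14 at 0 | 1 of 3 | 47 mL | 0.3 mL | 0.8 mL | 1.6 mL |
| On-drug Week 6 at 80 only | 2 of 3 | 80 mL | 1.1 mL | 2.7 mL | 5.3 mL |

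For example, 0.02 × 2/3 × 24 = 0.3 and 0.05 × 2/3 × 80 = 2.7. A simulation of the last two rows (212 per arm, SD 230 mL, r = 0.7, with a monotone maximum-likelihood fit standing in for the mixed model) gave biases within 0.1 mL of these figures. Applying BOCF to the affected group brought the bias to within about 0.1 mL of zero.

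**5. Scale.** 0.3/24.6 = 0.01 and 2.7/24.6 = 0.11 of a standard error. At 350 subjects, a true difference of 80 − 2.7 = 77.3 mL has power 0.882, against 0.902 for 80 mL (both by normal approximation).

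**6. What the other planned analyses cover.**

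- Sensitivity 1 uses the same trial-withdrawal grouping, and Sensitivity 3 imputes nothing.
- Sensitivity 2 (tipping point) keeps off-drug data and penalises all withdrawals whatever the reason, but runs only if the primary result is significant.
- Sensitivity 4 counts a missing Week 26 value as non-response, for that visit only.
- Supportive 6 and 7 sort by the reason for stopping drug, but drop data from more than 7 days after stopping.

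None keeps all observed off-drug data and applies BOCF by the reason for stopping drug.

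**The case against.** The choice of variable looks deliberate and can be defended. Under a treatment-policy estimand with off-drug data kept, a value is missing because the subject left, so the reason for leaving is a natural key. SAP 6.3 words the return-to-baseline argument in terms of leaving the trial, and Table 6 separates the two reasons on purpose. This stands, and it rules out calling the rule a plain contradiction of the SAP's rationale. If that rationale is pressed, it reaches everyone who leaves, including those who relocate. That is a separate argument about the list of reasons.

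A reader might also infer a breach of the protocol. Protocol 10.2.4 does not support that: its BOCF list includes tolerability, which suggests stopping drug, but its next sentence speaks of discontinuing the trial.

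A reader might infer that the error favours whichever arm has more such subjects. Under the planned control change of 0 mL, affected control subjects are modelled near 0, as BOCF would have them, so only affected mannitol subjects move the estimate. If the 50 mg control improves lung function, affected control subjects would offset part of the shift.

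The partial cover is real. Supportive 6 would give the example subject BOCF at Weeks 14 and 26, so a material effect would probably show there, though mixed with the effect of dropping other off-drug data. The tipping-point analysis runs exactly when a bias towards mannitol would matter most.

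What the objection leaves untouched is the group itself: subjects known to have stopped drug for a listed reason are handled as continuing to benefit, although the SAP aims not to favour mannitol.

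**Conclusion.** The point holds as a narrow gap of low to moderate priority. It concerns only visits after trial withdrawal, in subjects whose two recorded reasons differ.

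A reader might infer that such subjects are modelled as still enjoying the full drug effect. In general they are not: retained off-drug values pull the prediction down, to about 24 mL of 80 mL after one off-drug value at baseline. The 80 mL figure needs an average on-drug response as the only retained value, which is doubtful for someone stopping for lack of efficacy. Nor do the figures suggest a threat to the primary conclusion. The shift is about 0.3 to 2.7 mL towards mannitol, at most about 0.11 of the planned standard error.

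That size rests on an assumed 2% to 5% affected, a correlation of 0.7, one or two of three visits missing, and a true return to baseline off drug. Only the cross-tabulation of the two reasons would show whether the share is in that range.

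**What to change.** In SAP 6.3, SAP 8.1.1 and GRP2 of Sensitivity Analysis 1, keep the observed off-drug data as the primary rules already retain them. Apply BOCF to visits missing through trial withdrawal when either the trial-withdrawal reason or the recorded drug-discontinuation reason is adverse event, death, physician decision or lack of efficacy. At minimum, leave the primary rule as it is and add this as a sensitivity analysis. In both cases, cross-tabulate the two reasons by arm and report how many subjects change handling.

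The cost is about one sentence in each place, one more variable in the derivation and one table; both reasons are already collected. The estimate may become slightly less favourable to mannitol.

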## Statistical Analysis Plan

### 6.3. MISSING DATA

Missing or partial dates will be resolved in the most conservative manner. Additional details regarding partial or missing dates for the different safety data are given in Sections 6.2.1, 7 and 9 where applicable.

Details of imputation of missing values for efficacy endpoints are given in Section 8. Subjects who discontinue trial medication should remain in the trial and continue to provide all scheduled measurements. While all efforts will be made to ensure subjects remain in the trial, the following planned imputation strategy will allow for appropriate analyses of FEV1, FVC, ease of expectoration VAS score, and CFQ-R respiratory domain in the presence of missing data.

To calculate baseline values, missing Visit 1 measurements will be replaced by Visit 0 (screening) measurements, if available.

Missing post-baseline measurements as a result of withdrawal from the trial will be imputed in both ITT and PP analyses using an imputation using dropout reason (IUDR) methodology. For subjects who withdraw from the trial due to AE, death, physician decision, or lack of efficacy, missing post-baseline measures as a result of withdrawal from the trial will be imputed using the baseline measurement (baseline observation carried forward [BOCF] procedure). Missing measurements as a result of other causes of withdrawal from the trial (i.e. lost to follow-up, relocation, pregnancy, major protocol deviation, sponsor decision, withdrawal of consent, or other) will not be imputed. Missing data at intermediate visits (i.e. where data is available at a later visit) will not be imputed. Any measurements excluded from the PP analysis at the BDRM, and any derived variables based on these excluded measurements, will be treated as missing data but will not be included in the imputation process.

Imputation of missing FEV1 measurements by means of BOCF is a reasonable assumption in studies of adult subjects with CF, as those subjects who withdraw from the trial will no longer receive trial medication and are thus likely to promptly return to their baseline lung function. Imputation by BOCF specifically inhibits any assumed prolongation of an observed early trial medication benefit implicitly conferred by a mixed model.

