### 8.1.2. Sensitivity Analyses of the Primary Endpoint

To elicit insights into the effect of imputation via the planned BOCF+IUDR framework, the following sensitivity analyses of the primary endpoint will be conducted:

- Sensitivity Analysis 1: Pattern Mixture Model.
- Sensitivity Analysis 2: Tipping Point Analysis.
- Sensitivity Analysis 3: MMRM without imputation.
- Sensitivity Analysis 4: Responder Analysis.

As for the primary analysis, these sensitivity analyses target the de facto estimand assessing the effect of a treatment policy. These analyses will include all available on-treatment and off-treatment period data, regardless of adherence to or discontinuation of trial medication.

Planned approaches for handling missing data in Sensitivity analyses 1, 2, and 4 are not likely to favor the experimental arm (for more details see specific sections below.)

In the first 3 analyses, the mean absolute change from baseline FEV1 (L) over 26 weeks (including assessments at Weeks 6, 14 and 26) and at each post-baseline visit will be compared between the two treatment groups. For the responder analysis, the comparison between treatment groups will be performed at Week 26 (however subjects who withdraw from the trial earlier are assumed to be non-responders).

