## Statistical Analysis Plan

### 11. CHANGE FROM ANALYSIS PLANNED IN PROTOCOL

1. The analysis of spirometry endpoints has been updated to report relevant endpoints using L, as recorded in the CRF, rather than mL, as specified in the protocol, to keep consistency between data collection and final reporting.
2. The 4 hierarchical secondary endpoints and one non-hierarchical secondary endpoint listed below have been clarified to refer to PDPEs rather than PEs. All analyses will be repeated for PEs (defined as all events recorded on the PE Review CRF page that have associated antibiotic use) however the hierarchical testing will be based on the PDPE endpoints (Section 4.2):
  - Time to first PDPE.
  - Number of days on antibiotics (oral, inhaled, or IV) due to PDPE.
  - Number of days in hospital (admissions only) due to PDPE.
  - Rate of PDPE (per person year) over the 26-week treatment period.
  - Incidence of PDPEs over the 26-week treatment period.
3. The criteria to determine if a subject will be included in the PP set were adjusted during the BDRM and local major deviations were defined for the visit if the spirometry assessment was determined to be non valid, leading to the exclusion of all the specific assessment's data collected at the visit from the PP analysis. All the decisions made are documented in the [REDACTED] which will be finalized prior to unblinding the trial.
4. Time to event derivations will be based on date of randomization (Trial Day 1) for all subjects rather than date of first treatment (Treatment Day 1), except for time to discontinuation from trial medication, to allow consistency of derivations between randomized and treated and randomized but non-treated subjects.
5. Baseline FEV1 has been added as a continuous, fixed covariate in the REML based MMRM model, or the appropriate baseline value of the analysis variable (i.e. baseline percent predicted FEV1, baseline FVC, baseline VAS score, or baseline CFQ-R respiratory domain score).
6. For IUDR, BOCF imputations will be done for AE, death, physician decision, and lack of efficacy, while not for lost to follow-up; the logic behind this choice is the fact that motivation for the latter is not related to safety.

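### The SAP's claim that its missing-data handling does not favour mannitol is supported only for withdrawals imputed back to baseline

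*SAP*

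**What the plan says.** Protocol 10.2.4 already splits imputation by reason for leaving. It applies baseline observation carried forward (BOCF) to discontinuation for lack of efficacy, safety, tolerability or loss to follow-up, and leaves other causes un-imputed.

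SAP 6.3 and 8.1.1 keep the split but change the list. Section 11 item 6 discloses this: "BOCF imputations will be done for AE, death, physician decision, and lack of efficacy, while not for lost to follow-up". The reason given is that "the logic behind this choice is the fact that motivation for the latter is not related to safety". For the reasons off the list, SAP 8.1.1 states: "lost to follow-up, relocation, pregnancy, major protocol deviation, sponsor decision, withdrawal of consent, or other) will not be imputed".

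The rationale for BOCF is that "those subjects who withdraw from the trial will no longer receive trial medication and are thus likely to promptly return to their baseline lung function" (SAP 6.3), and that "Imputation by BOCF specifically inhibits any possible prolongation of an observed early treatment benefit implicitly conferred by a mixed model" (SAP 8.1.1). A direction argument follows, opening "Considering the higher drop-out rate observed with the experimental treatment compared to control in previous studies" and concluding that BOCF is unlikely to favour mannitol. The estimand paragraph then describes the primary analysis as "Handling missing data based on a clinically reasonable assumption not biased in favor of the mannitol arm". SAP 8.1.2 adds: "Planned approaches for handling missing data in Sensitivity analyses 1, 2, and 4 are not likely to favor the experimental arm".

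For withdrawals off the list, Sensitivity Analysis 1 imputes from completers of the same arm (GRP4 from GRP3, GRP6 from GRP5). The SAP says openly that this assumes the drug's benefit continues.

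**The concern.** The direction argument concerns BOCF. The two general statements cover all the missing-data handling, including subjects who do not receive BOCF. For them, higher drop-out on mannitol gives no protection. If they lose the benefit on leaving, as the SAP supposes, a model that carries the mannitol mean forward for them overstates the effect, and more drop-out makes this worse.

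The reason for removing loss to follow-up does not close the gap. Whether a departure is related to safety does not settle whether lung function returns to baseline afterwards, and lack of efficacy, also not a safety reason, stays on the list. The missing-at-random argument in Section 11 item 7 concerns missed intermediate visits, not withdrawal. Sensitivity Analysis 4, for its part, expects no benefit after withdrawal, whatever the reason.

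At stake is the size of the reported effect and a stated property of the analysis that readers may rely on. The false-positive rate is not at stake.

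**Working it through.** **1. The plan's own figure.** Protocol 10.1.1: 80 mL v 0 mL, SD 230 mL, two-sided 0.05, 90% power. n per arm = 2 × (1.960 + 1.282)² × 230² / 80² = 173.7, so 174 per arm and 348 in all, against 350 stated. Power at 175 per arm is 90.2%. The figure reproduces, and 80 mL is used below.

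**2. Which withdrawals each analysis returns to baseline or otherwise treats conservatively.**

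| Analysis | BOCF reasons | Loss to follow-up, consent withdrawal, residual category |
|---|---|---|
| Primary | baseline value | left to the mixed model |
| Sensitivity 1 | baseline model | own-arm completers (continued benefit) |
| Sensitivity 2, tipping point | shifted down | shifted down; only after a significant primary, and stops when significance is lost |
| Sensitivity 3 | left to the model | left to the model |
| Sensitivity 4, responder | non-responder | non-responder; Week 26 only |

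The general statements therefore hold for every withdrawal only in Sensitivity 2 and 4. Of the eight supportive analyses, 1 to 5 reuse the primary's handling, 8 imputes nothing, and 6 and 7 classify by reason for stopping medication, so someone who stopped for an adverse event and was later lost is returned to baseline there.

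**3. Share of visits missed.** Assume withdrawal is uniform over Days 0 to 183, with visits at Days 43, 99 and 183 (SAP 6.4, Table 4).
- No later visit attended: 43/183 = 0.235, 99/183 = 0.541, 183/183 = 1.000; mean 0.592.
- Next scheduled visit attended (Protocol 9.3): 0, 0.235, 0.541; mean 0.259.

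**4. Overstatement if leavers return to baseline.** Overstatement = share leaving × 80 mL × mean share of visits missed. Only the mannitol share matters, because the control change is 0 mL either way. The shares are assumed.

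| Share, three reasons | No later visit, formula | No later visit, simulated | Same, with a further 10% on BOCF | Next visit attended, simulated |
|---|---|---|---|---|
| 3% | 1.42 mL | 1.42 | 1.31 | 0.27 |
| 5% | 2.37 mL | 2.41 | 2.19 | 0.48 |
| 10% | 4.74 mL | 4.75 | 4.36 | 0.90 |

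The simulation used maximum likelihood for monotone missing data, SD 249 mL, an assumed within-subject correlation of 0.6 and equal shares in both arms; Monte Carlo SE was at most 0.04 mL. With the next visit attended, the formula gives 0.6, 1.0 and 2.1 mL. Those are upper figures, because the model also uses the off-drug value observed. Loss to follow-up alone at 1%, 2% or 5%, with no later visit: 0.5, 0.9 or 2.4 mL.

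**5. No true effect.** With 10% v 5% leaving, the simulated bias was 0.07 mL (SE 0.04) with no later visit and -0.01 mL (SE 0.01) with the next visit attended.

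**6. Scale.** SAP Section 10 reports a re-estimated size of 440 and 423 randomised; Protocol Table 7 ties 440 to an SD above 249 mL. SE at Week 26 = 249 × √(4/423) = 24.2 mL. For the three-visit average, 24.2 × √((1 + 2 × 0.6)/3) = 20.7 mL. So 4.7 mL is about 0.2 SE.

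**7. What the tipping point can show.** If 15% of mannitol subjects withdraw in all (assumed), each 20 mL step lowers the estimate by 0.15 × 20 × 0.592 = 1.8 mL, and the -0.080 L step by 7.1 mL. A second simulation took the first missed visit as equally likely to be any of the three, with SD 230 mL:

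| Mannitol BOCF / un-imputed; control BOCF / un-imputed | Return to baseline | SAP primary | Sensitivity 1 | Tipping point, control 0 / mannitol -0.080 L |
|---|---|---|---|---|
| 7% / 2%; 4% / 2% | 75.0 mL | 76.2 | 76.2 | 75.1 |
| 7% / 5%; 4% / 3% | 73.7 mL | 76.3 | 76.4 | 73.7 |
| 7% / 10%; 4% / 5% | 71.7 mL | 76.8 | 77.1 | 71.7 |

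That cell matches return to baseline for all reasons when the effect is 80 mL.

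**The case against.** The strongest reply has four parts.

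- **The split by reason is the protocol's design.** The list change is disclosed and predates unblinding, and the drop-out sentence itself speaks only of BOCF. This stands. The criticism is of the broader statements that follow.
- **Reason can bear on the premise.** Protocol 6.1.2 says the product is authorised in Europe for adults, so someone who relocates might still obtain it, while someone leaving for an adverse event has cause to stop. This stands as a reason why missing at random could be roughly right for some leavers. The SAP does not make that argument, and the documents do not say what leavers did.
- **All-reason return to baseline is nearly planned already, through the tipping point.** This stands in part. With a non-significant primary there is no positive claim to defend, and stopping before -0.080 L would itself reveal fragility. But the analysis is conditional, applies an assumed shift rather than a baseline model, and matches return to baseline only if the effect is near 80 mL.
- **The effect is small and rests on assumed shares.** This stands. The lower figures do, however, require attendance at the next visit, which a subject truly lost to follow-up is unlikely to manage.

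A reader might infer that the primary estimate is biased toward mannitol, or that the list was changed to help it. The documents support neither. Bias arises only if leavers lose benefit and the data are not missing at random. Physician decision was also added to the BOCF list, so the net direction of the change is unknown.

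**Conclusion.** The point holds in a limited form. The statement that the handling is not biased toward mannitol, and its counterpart for Sensitivity Analysis 1, are supported only for withdrawals imputed back to baseline. For the rest, the SAP's own premise points the other way.

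With 3% to 10% leaving for the three reasons and a true effect of 80 mL, the primary would be overstated by about 1.4 to 4.7 mL with no later visit and 0.3 to 0.9 mL with the next visit attended. That is at most about 0.2 SE over this range. With no true effect, or if missing at random holds, the bias is about zero. The shares, the uniform timing and the 0.6 correlation are assumptions; the 80 mL, the visit days and the 423 come from the documents.

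This is a worthwhile improvement rather than a threat to the trial's conclusion.

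**What to change.** 1. Add one variant of Sensitivity Analysis 1, run whether or not the primary is significant, in which every trial withdrawal is imputed from the baseline model (all of GRP4 and GRP6 moved to GRP2). Report it beside the primary, with withdrawals by reason and arm; SAP 7.1.2 already plans the breakdown by reason. Because it is multiple imputation, it avoids the understated variability that the SAP attributes to single imputation.
2. In the estimand paragraph of SAP 8.1.1, and in SAP 8.1.2 as it concerns Sensitivity Analysis 1, limit the wording to withdrawals given return-to-baseline imputation. It may stand for Sensitivity Analyses 2 and 4.
3. Optionally, to show the protocol's rule, run the primary mixed model with BOCF on the Protocol 10.2.4 list: loss to follow-up included, and physician decision only where it reflects safety, tolerability or lack of efficacy. A variant that moves loss to follow-up but keeps all physician decisions should not be described as restoring that list.

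The cost is a wording change and one or two extra runs, specified before unblinding. The added estimates may be a few mL less favourable. The primary analysis need not change.
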